2.2.2 Treatment Groups

During Part A, subjects will be treated in multiple dosing periods with single doses of a subset of the treatments -- Placebo, and 1mg, 3mg, 10mg, 30mg, 100mg, 300mg, or 600mg of LY. Dosing will be performed in a fasted state, except in the fourth dosing period for Cohort 2 when subjects will be dosed with 30mg LY after a standard meal. The treatment groups for Part A will be the dose levels of LY, plus the group 30mg LY fed.

During Part B, subjects will be enrolled in one of four dose-ascending groups (5mg LY, 20mg LY, 100mg LY, and 300mg LY) where they will be randomized to receive LY or placebo. The treatment groups for Part B will be Placebo, 5mg LY, 20mg LY, 100mg LY, and 300mg LY.

2.3 Handling of Dropouts and Missing Data

Summaries are primarily based on the Safety population, and safety data will be reported for all available subjects. In situations where Subjects in Part A discontinue early from the study, replacement subjects may be included for subsequent dosing periods.

Analyses of the PD endpoints will be performed using mixed-effects model repeated measures (MMRM). This methodology mitigates the impact of missing data, which will be assumed to be missing at random during the study.

Imputation of missing or partial dates is not expected, but if a complete date is required for calculations, the following algorithms will be applied:

- For the start date:
 - If year, month, and day are missing then use the minimum of the subject's first visit date or the consent date.
 - If either only month or month and day are missing then use January 1.
 - If only day is missing, impute the first day of the month.
- For the end date:
 - If year, month, and day are missing then use the subject's last visit date.
 - If either only month or month and day are missing then use December 31.
 - If only day is missing then use the last day of the month.
 - Do not expand the record past the subject's last visit.

The original missing or partial date, the imputed complete date, and the indicator variable identifying dates that were imputed will be retained in the database.

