7.2 Adverse Events

Investigators will monitor the safety of subjects and will be responsible for their medical care during the study. The investigator will interpret and document adverse events and will indicate whether each event is serious and the strength of causality to the study medication. The subject will be followed until adverse events are resolved.

Only those adverse events (AE) that emerge or worsen after the date of first dose of study medication, i.e. treatment emergent adverse events (TEAE), will be summarized. Adverse events with a missing start date will also be classified as TEAE.

Summaries of TEAE will include the number of subjects with at least one TEAE for each treatment group. When reporting by system organ class (SOC) and preferred term (PT), the reports will present the SOC in alphabetical order; while PTs within the SOC will be presented in order of overall decreasing frequency of occurrence in the combined LY treatment groups. A subject with multiple TEAEs (different PTs) coded to the same SOC will be counted only once for that SOC, but will be counted each time for different PTs within that SOC. A subject with separate events of the same PT (different start/stop dates) will be counted only once in the frequency tables for that PT.

In Part A, TEAEs will be reported using the treatment that the subject most recently received. Adverse events that occur on the first day of a dosing period will be assigned to the treatment received on that day.

No statistical testing will be performed for comparisons of TEAEs.

An overview of all TEAEs for both Parts A and B will also be provided by treatment group using the types of TEAEs defined in the following subsections.

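### Partial adverse event start dates are imputed as early as possible with no floor at first dose, so on-treatment events can be left out of the TEAE tables or, in Part A, credited to the wrong period

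*SAP*

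**What the plan says.** SAP 2.3 gives one start-date algorithm for all record types. It is conditional: "Imputation of missing or partial dates is not expected, but if a complete date is required for calculations", the listed rules apply.

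- Day missing: "If only day is missing, impute the first day of the month".
- Month, or month and day, missing: "If either only month or month and day are missing then use January 1".
- Date wholly missing: "use the minimum of the subject's first visit date or the consent date".

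End dates have a bound ("Do not expand the record past the subject's last visit"). Start dates have none.

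SAP 7.2 then restricts the tables: "Only those adverse events (AE) that emerge or worsen after the date of first dose of study medication" are summarized. It adds one safeguard: "Adverse events with a missing start date will also be classified as TEAE". It does not say whether a partial date counts as missing, or whether TEAE status is judged on the imputed date. For attribution: "In Part A, TEAEs will be reported using the treatment that the subject most recently received".

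**The concern.** Taking the earliest possible date is harmless for concomitant medications, because SAP 5 classifies them mainly by stop date. For adverse events it is not harmless. Deciding whether an event came after first dose is a date comparison, which is the situation in which SAP 2.3 calls for imputation. The imputed date is never later than the true one, so an on-treatment event can be pulled back before dosing, while a pre-dose event is never pushed forward.

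TEAEs are part of the primary endpoint (Protocol 11.3.1.2), and the groups are small: 8 LY subjects per Part B cohort and 6 per Part A dose level. If partial dates follow SAP 2.3, an event with a partly known date is also handled less cautiously than one with no date, which SAP 7.2 counts as treatment-emergent.

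In Part A, doses are about two weeks apart (Protocol 6.1.1). The same backward shift can therefore carry an event into an earlier dosing period and so to a different treatment.

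**Working it through.** The documents give no figure for this point, so there is none to reproduce. Every share below is conditional on a partial start date and on the imputed date being used.

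**Assumptions not in the documents.** Dosing day and onset are uniform. First dose means the first LY or placebo dose, as the 29-day maximum exposure in SAP 7.1.1 implies. An imputed date equal to the first-dose date counts as a TEAE.

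**Part B, day missing, 30-day month.** Dosing runs over Days 1 to 29 (Protocol 8.1). If first dose falls on day m, an onset in the same month is imputed to day 1 of that month.

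- m = 1: the imputed date equals first dose, so 0 of 29 onset days are lost.
- m = 2 to 30: (31 − m) of 29 are lost. That is 29/29 on the 2nd, 16/29 on the 15th and 1/29 on the 30th.
- Average: (29 + 28 + … + 1)/(30 × 29) = 435/870 = 50%.
- If after first dose is read strictly, the m = 1 tie is also lost: (435 + 29)/870 = 464/870 = 53%.

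**Same formula, shorter onset windows.** With a window of w days, the share is the sum over m = 2 to 30 of min(w, 31 − m), divided by 30w.

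- w = 14: (16 × 14 + 91)/420 = 315/420 = 75%.
- w = 7: (23 × 7 + 21)/210 = 182/210 = 87%.

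**Check on real calendar months.** First-dose dates were spread over 365 days from 1 July 2016, shortly after the amendment approval date of 22 June 2016 in SAP 1.1. The shares lost are 50.7% (Days 1 to 29), 75.3% (first 14 days) and 86.8% (first 7 days).

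**Part B, January 1 rule.** On the same calendar, 95.9% of Day 1 to 29 onsets move before first dose. The share is 100% if dosing starts in July to October 2016, because January 1 of that year always precedes first dose.

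**Part A, day missing.** Doses are 14 days apart and onset falls within 14 days of each dose.

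| True period | Dated before first dose | Moved to an earlier period | Correct |
|---|---|---|---|
| 1 | 75.3% | – | 24.7% |
| 2 | 29.3% | 46.0% | 24.7% |
| 3 | 0.5% | 74.9% | 24.7% |
| 4 (Cohort 2) | 0% | 75.3% | 24.7% |

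**Direction of one-period shifts** (sequences in Protocol Figure GSEA.1).

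- Cohort 1: 2 of 6 go up in dose (placebo to 10 mg, placebo to 1 mg).
- Cohort 2: 4 of 9 go up (placebo to 30 mg, placebo to 3 mg, placebo to 300 mg, 30 mg fed to 300 mg).
- The others go down, for example 100 or 300 mg to placebo, or 300 mg to 30 mg.

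**Weight of one event.** A lost subject-event is 1/8 = 12.5 percentage points in a Part B LY group and 1/6 = 16.7 points at a Part A dose level, if that subject has no other qualifying event.

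**The case against.** The strongest reply is that the problem may never arise. SAP 2.3 does not expect imputation. Part A subjects are confined around dosing and seen again on Days 3 and 5. Part B has confinement, visits on Days 7, 14 and 21, and attempted telephone calls that ask about adverse events. Original partial dates and imputation flags are kept, events are listed, and no TEAE comparison is tested. A missing start date in SAP 7.2 could also be read to include a partial one, and Protocol Appendix 1 defines a TEAE by comparison with the pretreatment state, without mentioning imputed dates.

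This limits the likely total effect but leaves the gap open. Much Part B dosing is at home, where incomplete onset dates can occur. SAP 7.2 does not settle the partial-date case, so two programmers could code it differently.

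Three stronger readings are tempting, and the documents do not support them.

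- A reader might infer that Part A events shifted to an earlier period disappear. They remain after first dose and stay in the TEAE tables under the wrong treatment.
- A reader might infer that the shift always lowers the apparent dose. The sequences show moves both ways.
- A reader might see SAP 2.3 and 7.2 as contradictory on wholly missing dates. SAP 7.2 is the specific rule and needs no date, so it governs TEAE status. It leaves open only which Part A period such an event belongs to.

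**Conclusion.** The gap is real and should be closed. Applied as written, SAP 2.3 can place a partial-date on-treatment event before first dose, and SAP 7.2 then omits it from the tables for the primary endpoint. Conditional on a day-missing date in Part B, about half of Day 1 to 29 onsets are affected. The share for an individual subject runs from none to all, depending on the calendar day of first dose. Under the January 1 rule nearly all are lost.

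The averages rest on uniform dosing day and onset, and the whole point rests on the imputed date being used for TEAE status, which the SAP neither states nor excludes. Few such dates are expected, so the total effect is probably small. The TEAE error runs only toward undercounting, for placebo as well as LY. The Part A error is misattribution with no fixed dose direction.

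**What to change.** Add an adverse event rule to SAP 2.3 and refer to it in 7.2.

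- **TEAE status.** An event with a missing or partial start date counts as a TEAE unless the known parts show onset before first dose. Set the imputed date to the later of first dose and the earliest date compatible with the known parts. In the calendar check this brings dropped on-treatment partial-date events to 0% in both parts.
- **Part A attribution.** The floor alone still leaves about 75% of day-missing events from Periods 2 and 3 in an earlier period (Period 2: 29.3% + 46.0% = 75.3%). If more than one dosing period is compatible, or the date is wholly missing, attribute the event for tabulation to the highest LY dose received in a compatible period and flag it in the listing. State a tie-break for the Cohort 2 sequence that receives 30 mg both fasted and fed. Assigning to the latest compatible treatment would not do, since it can move an active-dose event to placebo or a 300 mg event to 30 mg fed.
- **Concomitant medications.** Keep the current start-date rule.

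The cost is a few sentences and some programming. A few pre-dose events may be counted as TEAEs, and a few placebo or lower-dose events may be credited to a higher dose. Both errors are in the conservative direction, and SAP 7.2 already accepts the first for missing dates.

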2.4 Adjustment for Multiple Centers

Part A will be conducted in a single study center.

Part B will be conducted in multiple study centers, but PRA will centrally manage the randomization. No adjustment of multiple study centers will be incorporated into the statistical analyses for this study. This is common for early phase studies with limited enrollment.

2.5 Interim Analysis and Adjustment for Multiplicity

Not applicable.

2.6 Coding of Concomitant Medications and Adverse Events

Adverse events (AEs) will be coded using version 19.0 of the Medical Dictionary for Regulatory Activities (MedDRA™), and concomitant medications will be coded using the Mar-2016 version of the World Health Organization Drug Dictionary. The version of the dictionary used for reporting will be provided in the CSR.

2.7 Definition of Study Time Points

Study day is explicitly defined in the study protocol.

2.8 Reporting Conventions

This section details the general conventions to be used for the statistical analyses. Departures from these general conventions will be provided in the specific detailed sections of this analysis plan. The following conventions will be applied to all data presentations and analyses:

- Continuous variables will generally be summarized by the number of subjects, mean, standard deviation, median, minimum, and maximum.
- Categorical variables will be summarized by the number and percentage of subjects within each category.
- All mean and median values will be formatted to one more decimal place than the measured value.
- Standard deviation values will be formatted to two more decimal places than the measured value.
- Minimum and maximum values will be presented with the same number of decimal places as the measured value.
- The number and percent of responses will be presented in the form XX (XX %), where the percentage is in parentheses. Percentages will be rounded to the nearest percent. In the case of a frequency of zero, the frequency and percentage will be presented as 0 rather than 0 (0%).
- All summary tables will include the analysis population sample size (i.e., number of subjects) in each treatment group.
- Date variables will be formatted as ddMMYY for presentation.

3 Subject Accounting and Disposition

3.1 Subject Accounting

The number of subjects in the Safety and PD populations will be presented by treatment group. For each treatment group the date of the first subject visit and the last subject visit will also be provided. These dates and subject totals will also be summarized by study site for Part B. In addition, the total number of subjects randomized and the number of subjects added as replacements will be presented by cohort for Part A.

A list of protocol violations that could potentially impact the analysis of the study will be determined during the conduct of the study by study team members who are blinded to study treatment being received. The number and percentage of subjects with each violation will be tabulated overall and by randomized treatment assignment for Part B.

3.2 Study Disposition

The disposition of all randomized subjects will be presented. The number of subjects in the Safety Population will be presented overall and by treatment group. In addition, the reason for study discontinuation will be tabulated for the overall population and by treatment group using the list of reasons provided in the eCRF.

For Part A the disposition of all subjects in the Safety Population will be presented. Since subjects receive multiple treatments during the course of the study, the number (percent) of subjects who complete a treatment period will be presented. The number (percent) of subjects who discontinue from the study will be tabulated according to the most recently received treatment. The reason for study discontinuation will also be tabulated using the list of reasons provided in the eCRF. Denominators for all percentages in the table will be the number of subjects in the Safety Population who received the given treatment.

For Part B the disposition of all randomized subjects will be presented. Randomization of subjects for Part B occurs early, on Day -7, so that subjects can be allocated evenly to treatment with simvastatin or atorvastatin for the DDI component of the study. The number of subjects randomized, the number of subjects randomized but not treated with LY or placebo, and the number of subjects added as replacements will be summarized by treatment assignment and overall for each statin and the combined statin assignment. The reason for discontinuation for subjects who were randomized but not treated with LY or placebo will only be presented in data listings.

The number (percent) of subjects who complete Part B of the study, and the number (percent) of subject who discontinue, along with the reason for discontinuation, will be summarized by treatment group and overall. Denominators for all percentages in the table will be the number of subjects in the Safety Population.

4 Baseline Characteristics

Demographic data, baseline anthropometric measurements, and fasting lipids will be summarized at the subject level using descriptive statistics for the overall study population and by treatment group for both Parts A and B. These summaries will be based on the Safety population. Subjects who are missing measurements of the baseline variable being analyzed will not be included in the summary for that variable.

4.1 Demographics

Demographic variables collected prior to randomization include date of birth, sex, race, and Hispanic ethnicity. Age at study entry, age group, sex, and race will be summarized and reported. Age at study entry will be based on the age of the subject on the date the informed consent is signed. Age group will be defined using the median age group for the Safety population (Age <= Median age; Age > Median age). Subject race will be reported using the categories provided in the eCRF (i.e., American Indian or Alaskan Native, Asian, Black or African American, Native Hawaiian or other Pacific Islander, and White). The responses for Hispanic ethnicity are Hispanic or Latino and Non-Hispanic or Latino.

4.2 Baseline Anthropometrics

Subject height and weight will be collected prior to randomization for both Parts A and B. Both variables will be reported in metric units (height in cm and weight in kg) and will be summarized as continuous variables along with Body Mass Index (BMI; in kg/m²). Body mass index will also be analyzed categorically using the categories overweight ($25 \leq \text{BMI} < 30 \text{ kg/m}^2$) and Class 1 Obese ($30 \leq \text{BMI} < 35 \text{ kg/m}^2$) that are provided by United States Center for Disease Control (<http://www.cdc.gov/obesity/adult/defining.html>).

In Part B the additional anthropometric variables waist, hip, and neck circumference (all in cm) will be collected on Day -1 of the study. These variables will also be summarized as continuous variables for each of the treatment groups and overall.

4.3 Baseline Lipids

For enrollment in Part B subjects are required to have screening triglyceride (TG) levels between 150 and 499 mg/dL, inclusive, and screening low-density lipoprotein cholesterol (LDL-c) levels between 100 and 200 mg/dL, inclusive. These lipids levels are allowed for enrollment in Part A but they are not required. During the Part B screening visit, fasting measurements of TG, total cholesterol (TC), and high-density lipoprotein cholesterol (HDL-c) will be obtained from plasma samples. LDL-c and non-HDL-c will then be derived as follows:

$$\text{LDL-c} = \text{TC} - (\text{TG}/5 + \text{HDL-c}), \text{ and}$$

$$\text{non-HDL-c} = \text{TC} - \text{LDL-c}.$$

Descriptive statistics for these five lipid parameters for subjects enrolled in Part B will be provided for each of the treatment groups and overall.

5 Concomitant Medications

Concomitant medications will be defined as medications, other than simvastatin and atorvastatin, taken on or after the date of first dose of randomly assigned study treatment (LY or placebo). This includes all medications initially taken prior to the date of first dose of randomly assigned study medication but with a stop date that is either missing or after the date of first dose of randomly assigned study medication. Those medications where the stop date is documented as prior to the date of first dose of randomly assigned study medication will be classified as prior medications. The prior medications will not be included in any summary reports.

The number (percent) of subjects who receive each concomitant medication, based on the WHODD preferred drug name, will be tabulated for Part B, but it is not planned to summarize in table format the concomitant medication usage for Part A of the study. However, by-subject listings of all concomitant medications that includes WHODD preferred drug name will be prepared separately for Parts A and B.

6 Pharmacodynamics Analyses

Pharmacodynamics (PD) analyses for this study will be based on fasting and post-prandial lipid profiles, fasting free fatty acids (FFA), β -hydroxybutyrate, apolipoprotein (Apo) B100, ApoC3,

proprotein convertase subtilisin/kexin type 9 (PCSK9), lipoprotein (a) [Lp(a)] and insulin, and body weight. All of these assessments will be collected longitudinally during the study.

All PD analyses will be performed using the PD population. Presentations of PD analyses will include the number of subjects with data at each time point plus related statistics derived from the analysis. Subjects who received Placebo during more than 1 dosing period in Part A will have their data from different dosing periods reported separately. The following sections contain the planned analyses. If plots of the raw data or residuals suggest alternative analysis techniques, such as log-transformation or nonparametric methods, then additional analyses will also be performed. The rationale for and results of the alternatives techniques will be described in the CSR.

